8.4 Washout (Days 29-42)

The first treatment period will be followed by a washout period of two weeks (Days 29 to 42 inclusive). Subjects will continue their NPRS diary entries each evening, but will not take any IMP.

8.5 Second baseline period (Days 43-49)

During the second baseline period (Days 43 to 49 inclusive), subjects will continue their diary entries and will not take any IMP. They will record their NPRS rating each evening.

8.6 Second treatment period (Days 50-77), Visits 5 to 7

Subjects will return to the unit on Day 50 (± 1) with their diary completed from Days 29 to 49 inclusive and with their medication bottle.

8.6.1 Day 50 (± 1), Visit 5

Subjects will return on Day 50, and the following assessments will be undertaken:

- Review of the subject's pain diary (Days 43-49 inclusive)
- Weight
- ECG
- Vital signs
- Targeted physical examination, including assessment of area of pain
- · Concomitant medications
- Blood and urine samples for safety analysis (haematology, clinical chemistry, urinalysis)

Results from safety monitoring tests are not required prior to dosing. Subjects will also complete their second baseline assessments for Patient Reported Outcomes:

- Interference scale of short form BPI
- SF-MPQ-2
- NPSI
- BDI-II

In PK subjects, a pre-dose NPRS will be completed (maximum one hour before dosing) and a pre-dose blood sample taken for PK analysis. QST subjects will have a pre-dose QST assessment, if not completed within the previous 7 days.

Subjects (except for PK subjects) will take their allocated IMP and will remain in the clinic for up to one

hour to check for adverse events. Vital signs will be measured 30 (+/-10) minutes after IMP dosing.

PK subjects will take their allocated IMP and will remain in the clinic for at least 6 hours. At scheduled times (2, 5, 15, 30, 60 minutes, 2, 4 and 6 hours after IMP dosing), blood samples will be taken for PK analysis. NPRS will be monitored at 0.5, 1, 2, 4 and 6 hours. Vital signs will be measured 30 (+/-10) minutes after IMP dosing.

All subjects will leave the unit with sufficient IMP for the second treatment period. They will be reminded to complete their NPRS diary each evening.

8.6.2 Day 63 (± 1), Visit 6

On Day 63 (Visit 6), subjects will take their morning IMP dose and return to the clinic with their medication bottle. The following assessments will be undertaken:

- Weight
- Vital signs
- Targeted physical examination
- Concomitant medications
- Adverse events
- Compliance with medication
- Compliance with diary entries

Subjects will be reminded to continue their medication and to record daily entries into their diary. They will be asked to return on Day 77 with their medication bottle, but without taking their morning dose of IMP. They will also be reminded not to take paracetamol within 4 hours of the next clinic visit.

8.6.3 Day 77 (± 1), Visit 7

On the morning of Day 77 (Visit 7, Last Day of Second Treatment Period), subjects will not take their morning dose of IMP. They will return to the clinic with their medication bottle and the following assessments will be undertaken:

- Weight
- ECG
- Vital signs
- Targeted physical examination
- · Concomitant medications
- Blood and urine samples for safety analysis (haematology, clinical chemistry, urinalysis)
- Adverse events
- · Compliance with medication
- Compliance with diary entries

Subjects will also complete assessments for Patient Reported Outcomes:

- Interference scale of the short form BPI
- SF-MPQ-2
- NPSI
- BDI-II

• PGIC

Subjects (except PK and QST subjects) will take their morning dose of IMP and leave the clinic. They will take their second Day 77 IMP dose in the evening and then discontinue treatment.

In PK subjects, a pre-dose NPRS will be completed (maximum one hour before dosing) and a pre-dose blood sample will be taken for PK analysis.

PK subjects will take their first dose of IMP and remain in the clinic for at least 6 hours. At scheduled times (2, 5, 15, 30, 60 minutes, 2, 4 and 6 hours after IMP dosing), blood samples will be taken for PK analysis. NPRS will be monitored at 0.5, 1, 2, 4 and 6 hours. They will leave the clinic and take their second Day 77 IMP dose in the evening. They will then discontinue treatment.

QST subjects will take their morning dose of IMP and will have QST parameters assessed 2 hours after this dose. They will leave the clinic and will take their second Day 77 dose in the evening. They will then discontinue treatment.

All subjects will be asked to bring their medication bottle to the End of Study visit.

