9.1 Primary endpoint

Absolute change in mean pain score, using an 11 point NPRS, from baseline to the last week of
each treatment period. Pain is recorded once daily in a subject diary in the evening, and should
reflect the subject's average pain over the last 24 hours

Baseline mean pain for each subject is defined as the mean of the last five available ratings of daily pain, recorded in each baseline period.

End of treatment mean pain for each subject is defined as the mean of the last five available ratings of daily pain, recorded in the last 7 days of each 4 week treatment period.

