10.4 Study Periods

Duration between initial screening and end of first treatment (Days -28 to 28) is considered as study period 1; washout (Days 29 to 42) is considered as washout period; duration between second baseline period up to end of study visit (Days 43 to 91) is considered as study period 2. Study periods will be considered to set analysis visits.

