10.12.2 Efficacy Endpoints

Baseline will be derived for efficacy endpoints within each study period:

- Period 1 baseline:
- NPRS score: Mean of the last five available ratings of daily pain recorded in baseline period 1.

- NPRS score with timepoints: For subjects with NPRS collected at timepoints in baseline and week 4 visits, baseline will be defined as the pre-dose assessment at the respective visit.
- Secondary Efficacy endpoints: Latest measurement taken prior to Day 1 dosing.
- Period 2 baseline:
- NPRS score: Mean of the last five available ratings of daily pain recorded in baseline period 2. If there are less than 5 ratings in baseline period 2, then baseline from period 1 will be considered.
- NPRS score with timepoints: For subjects with NPRS collected at timepoints in baseline and week 4 visits, baseline will be defined as the pre-dose assessment at the respective visit. If pre-dose assessment is missing, then pre-dose assessment from the respective visit in period 1 will be considered.
- Secondary Efficacy endpoints: Latest measurement taken on/after Day 43 and prior to Day 50 dosing. If baseline measurement is missing in period 2, then baseline from period 1 will be considered.

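### Day 49 is both an IMP-free baseline day and a permitted first-dose day, so a post-dose rating can enter the Period 2 NPRS baseline

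*Protocol*

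**What the plan says.** - **IMP-free days.** Protocol 5.1 and SAP 4.5 exclude IMP on Days 29 to 49. Protocol 8.5 repeats this for the baseline week: "During the second baseline period (Days 43 to 49 inclusive), subjects will continue their diary entries and will not take any IMP".
- **Visit 5 window.** Protocol 8.6: "Subjects will return to the unit on Day 50 (± 1) with their diary completed from Days 29 to 49 inclusive". The schedule (protocol 2.2) gives the same ± 1 day, but no tolerance for the second baseline column.
- **Dosing at Visit 5.** Protocol 8.6.1: "Subjects (except for PK subjects) will take their allocated IMP and will remain in the clinic". PK subjects are also dosed at this visit and stay longer.
- **Time of rating.** Protocol 8.5: "They will record their NPRS rating each evening".
- **Primary baseline.** Protocol 9.1 uses "the mean of the last five available ratings of daily pain, recorded in each baseline period". SAP 10.12.2 has "Mean of the last five available ratings of daily pain recorded in baseline period 2". Neither requires the ratings to precede the first dose. The same SAP section does require this for the Period 2 baselines of the secondary endpoints, although it ties the condition to nominal Day 50.
- **Analysis weeks and periods.** SAP 10.3 sets weeks as fixed study days (Period 1 Week 4 is Days 22-28). SAP 10.4 does the same for periods: "washout (Days 29 to 42) is considered as washout period".
- **Visit 4 window.** Protocol 8.3.3 allows Day 28 ± 1. The morning dose is taken in clinic and the period's last dose that evening.

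**The concern.** The visits that start and stop treatment can move by a day, but the analysis windows that depend on them cannot. A subject who attends Visit 5 on Day 49 is dosed at the clinic and rates pain that evening. That rating falls inside Days 43-49 and, being the latest, is always among the last five if it was recorded.

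The Period 2 change from baseline supplies one half of every within-subject comparison in the primary analysis. A treated rating in the baseline moves that baseline towards the on-treatment level and shrinks the Period 2 change. Period 1 does not have this problem, because Day 1 has no window. If the rule is not settled before database lock, someone will have to decide case by case whether a Day 49 rating belongs in the primary baseline.

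Visit 4 raises a related problem at the end of Period 1. If it falls on Day 27, treatment stops that evening, yet the Day 28 rating still counts in Week 4, the primary time point.

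**Working it through.** **1. The plan's own figure.** Inputs (protocol synopsis and 13.2): difference 1, SD of change 2, correlation 0.5, two-sided 5%, 44 evaluable.

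- SD of the within-subject difference = √(2 × 2² × (1 − 0.5)) = 2.0.
- Noncentrality = 1 / (2/√44) = 3.317. The noncentral t distribution with 43 df gives power 0.900, so the stated 90% is reproduced. This point does not dispute it.

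**2. Day counts over the permitted visits.** IMP-free days = (first Period 2 dose day) − (last Period 1 dose day) − 1. Washout days to Day 42 = 42 − (last Period 1 dose day).

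| Last Period 1 dose | First Period 2 dose | IMP-free days | Washout days to Day 42 | Untreated days in 43-49 |
|---|---|---|---|---|
| 28 | 50 | 21 | 14 | 7 |
| 28 | 49 | 20 | 14 | 6 |
| 29 | 50 | 20 | 13 | 7 |
| 29 | 49 | 19 | 13 | 6 |

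An early Visit 5 removes one untreated baseline day and leaves the washout at 14 days. Only a late Visit 4 puts IMP inside Days 29-42.

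**3. The diary requirement.** A Day 49 attendee is asked to arrive with the diary complete through Day 49, but that day's entry is not due until the evening. The instruction cannot be met at a daytime visit.

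**4. Weight of the affected rating.** It is one of five, or 20%. Let e be the first-day drug effect over placebo that shows in the Day 49 rating. An affected subject's baseline then shifts by e/5.

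**5. Dilution of the 1-unit difference.** The documents give neither e nor the fraction f of subjects dosed on Day 49, so both are assumed. With half of those subjects on LAT8881 in Period 2 and no baseline adjustment, dilution = f × ½ × e/5. Power is recomputed at n = 44 with the SD unchanged.

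| f | e | Dilution | Remaining difference | Power |
|---|---|---|---|---|
| 10% | 0.25 | 0.0025 | 0.9975 | 0.899 |
| 25% | 0.5 | 0.0125 | 0.9875 | 0.893 |
| 50% | 0.5 | 0.025 | 0.975 | 0.885 |
| 100% | 1.0 | 0.10 | 0.90 | 0.831 |

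The last row needs every subject dosed on Day 49 and a full effect on the first day. It is a bound and should not be read as an expectation.

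**6. Week 4 in Period 1.** With Visit 4 on Day 27, Days 22-28 hold six treated days and one untreated day. The Day 28 rating, if made, is the latest and so also carries weight 1/5 in the end-of-treatment mean.

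**The case against.** The documents bar IMP on Day 49 in several places, and the diary instruction presupposes that Day 49 has passed before Visit 5. One can therefore argue that Day 49 dosing is not truly permitted, or that a post-dose rating lies outside a baseline period defined as IMP-free. This has some force: the passages contradict each other and do not plainly license Day 49 dosing. But neither document says which passage prevails, and neither shifts the baseline or week labels to actual dose dates. Blinded review before lock (SAP 9 and 9.2) could catch a case, but no rule there covers it.

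The objection on size largely stands. The rating covers the previous 24 hours. If dosing were about 12 hours before the rating (an assumption), roughly half of the recalled period would be untreated. The primary model also includes baseline as a covariate, which offsets part of any shift.

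A reader might infer more than the documents support:

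- **That Day 49 dosing shortens the two-week washout.** It does not. Days 29-42 stay at 14 days, and the 13-day figure comes only from a late Visit 4. Even then the schedule (protocol 2.1) allows ± 1 day at each end of the washout, and the 19-day minimum IMP-free interval still exceeds the two weeks justified in protocol 5.2.
- **That an affected subject loses 0.2 units.** That requires the full 1-unit effect at once and ignores both the 24-hour recall and the baseline adjustment.
- **That a Day 51 visit does similar harm.** The untreated Day 50 rating is the first of seven Week 1 days. It enters the last five only if at least two of Days 51-56 are missing, and it concerns a secondary time point.

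**Conclusion.** The concern holds as a conflict between visit windows and fixed analysis days. Day 49 is an IMP-free baseline day in protocol 5.1 and 8.5 and SAP 4.5, and an in-window dosing day in protocol 8.6, 8.6.1 and the schedule. As written, the primary NPRS baseline would accept a post-dose rating on that day, a gap the SAP closes for the secondary endpoints. The Day 28 rating after a Day 27 Visit 4 is the same kind of fault. Separately, a Day 29 Visit 4 places IMP inside the stated washout.

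The effect is small. It is at most one fifth of any first-day effect, only in subjects seen on Day 49, and less once the recall period and baseline adjustment are considered. Under the assumed 25% of subjects and 0.5-unit effect, power falls by about 0.007. The documents do not show that any subject was dosed on Day 49. The sample size of 44 needs no change. The reason to act is that the rule governs the primary endpoint and costs almost nothing to settle in advance.

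**What to change.** **Baseline (protocol 9.1; SAP 10.4 and 10.12.2).** Define the Period 2 NPRS baseline as the last five available ratings in the seven evenings before the actual first Period 2 dose, using only ratings made before that dose. The window becomes Days 42-48, 43-49 or 44-50 for Visit 5 on Day 49, 50 or 51.

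**Treatment weeks (SAP 10.3).** Count weeks from the actual first dose in each period. For subjects who reach Week 4, end it at the actual last dose. With Visit 4 on Day 27, the SAP should say whether Week 4 is then Days 22-27 (six evenings) or the seven evenings ending on Day 27, which would share Day 21 with Week 3.

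**Reconciliation.** The passages on the Visit 4 and Visit 5 windows, the IMP-free days and the washout days must be made to agree. Which clinical rule should prevail is for the sponsor; none is proposed here.

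**Cost.** Wording changes and a date-based derivation, with no added visits or data: diary ratings already run every evening through washout, and treatment duration in SAP 10.14 already uses first and last dose dates. The downside is that, for a Day 49 visit, the baseline window reaches back to Day 42, a washout day that is still untreated. Simply deleting the Day 49 rating would avoid that but leave six evenings. Two missed entries would then trigger the SAP's substitution of the Period 1 baseline, whereas seven evenings tolerate two.

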On Day 50, subjects will return to the clinic and cross over to receive the second treatment (either LAT8881 or placebo, whichever treatment was not received in the first treatment period) twice daily for four weeks (Days 50 to 77). On the morning of Day 77, they will return to the clinic for their end of second treatment visit and will take an IMP capsule in the morning during their clinic visit. They will take their final IMP dose for this treatment period in the evening.

Subjects will return to the clinic on Day 91, two weeks after their last treatment visit, for an end of study visit.

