8.7 End of Study visit

8.7.1 Day 91 (± 2) Visit 8

At the end of study visit, subjects will return with their medication bottle. The following assessments will be undertaken:

- Weight
- Vital signs
- Targeted physical examination
- Concomitant medications
- Blood and urine samples for safety analysis (haematology, clinical chemistry, urinalysis)
- Adverse events

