10.3 Visits

Analysis visits will be defined as follows within each study period:

Visit as per Protocol	Study Period	Analysis Visit
Visit 1 (Days -28 to -1)	Pre-Treatment	Screening

Day 1, Visit 2	Period 1	Visit 2/Visit 5
Day 14, Visit 3	Period 1	Visit 3/Visit 6
Day 28, Visit 4	Period 1	Visit 4/Visit 7
Day 50, Visit 5	Period 2	Visit 2/Visit 5
Day 63, Visit 6	Period 2	Visit 3/Visit 6
Day 77, Visit 7	Period 2	Visit 4/Visit 7
Day 91, Visit 8 or Early Termination	-	EOS / Early Termination

For NPRS scores, post-baseline summaries will be based on weeks within study:

- Week 1 (Days 1-7 and 50-56)
- Week 2 (Days 8-14 and 57-62)
- Week 3 (Days 15-21 and 63-69)
- Week 4 (Days 22-28 and 70-76)

Timepoints will be included for NPRS data as ‘Pre-dose’ and ‘X hours post-dose’ for subjects with measurements taken at timepoints. NPRS will be derived using diary scores as detailed in Section 10.15.

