10.15 Efficacy Endpoints

10.15.1 NPRS Mean Scores

NPRS mean daily score ranging from 0 (no pain) to 10 (worst imaginable pain) will be derived at baseline and weeks 1 to 4 for each treatment period. Baseline mean score is defined in Section 10.12.2. The mean daily pain score each week during treatment is the arithmetic mean of the last 5 available ratings of daily pain recorded in each 7 day period within each treatment period. Standard deviations (SD) of the mean scores will be included in analyses datasets. If a subject has <5 non-missing ratings, the mean score will be set to missing for the respective week.

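### SAP 10.3 builds the primary endpoint from different treatment days in the two periods, and once it is corrected the Day 77 evening rating has no stated route back to the site

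*Protocol*

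**What the plan says.** **Window.** Protocol 9.1, repeated in SAP 7.1, averages the last five available daily ratings "recorded in the last 7 days of each 4 week treatment period". Ratings are made in the evening. Protocol 5.1 gives the second treatment "twice daily for four weeks (Days 50 to 77"), so the two windows are Days 22-28 and Days 71-77.

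**SAP day ranges.** SAP 10.3 prints "Week 4 (Days 22-28 and 70-76") and, earlier in the same list, "Week 2 (Days 8-14 and 57-62"). Day 77 is in no week.

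**Minimum.** SAP 10.15.1: "If a subject has <5 non-missing ratings, the mean score will be set to missing for the respective week". The protocol has no such minimum. SAP 8.1 leaves imputation for the primary endpoint to the blinded review meeting.

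**Diary after Visit 7.** Protocol 8.6.3 places Visit 7 on the morning of Day 77 (± 1) and checks diary compliance there. It ends: "All subjects will be asked to bring their medication bottle to the End of Study visit". Section 8.7.1 begins: "At the end of study visit, subjects will return with their medication bottle", and lists no diary item. In schedule 2.2 the NPRS row is blank at Visit 8. The V3 amendment entry records that the diary is not electronic.

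**Diary after Visit 4.** Protocol 8.3.3 tells subjects to keep making entries, and 8.6 has them return on Day 50 "with their diary completed from Days 29 to 49 inclusive and with their medication bottle". The Day 28 evening is not named.

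**Visit-day entry.** The synopsis has subjects make a diary entry on the mornings of Days 28 and 77 before attending. Protocol 8.3.3, 8.6.3, 9.1 and 10.5.1.1 provide only for an evening entry.

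**The concern.** The primary comparison is within subject, so the endpoint should be built in the same way in both periods. As printed, the SAP does not do this. The Period 2 ranges look like a day-count slip that starts at week 2.

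The obvious correction, Days 71-77, brings in a rating that is made after the last visit at which the diary is checked. If that entry is not brought back, the five-rating minimum is applied to seven possible evenings in Period 1 but six in Period 2 at the nominal visit day. Missing primary values would then depend on the period and on the exact date of Visit 7.

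**Working it through.** **1. The plan's sample size.** Inputs from Protocol 13.2 and the synopsis: SD of change 2, correlation 0.5, difference 1, two-sided 5%, power 90%. SD of the within-subject difference = √(2 × 2² × (1 − 0.5)) = 2. The normal approximation gives (2 × (1.960 + 1.282) / 1)² = 42.03, rounded up to 43. The paired t calculation gives power 0.900 at n = 44, and 44 / 0.80 = 55. The stated 44, 90% and 55 reproduce.

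**2. Day ranges as treatment days.** Period 2 treatment day = study day − 49.

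| Week | Period 1 | Period 2, study days as printed | Period 2, treatment days | Length |
|---|---|---|---|---|
| 1 | 1-7 | 50-56 | 1-7 | 7 |
| 2 | 8-14 | 57-62 | 8-13 | 6 |
| 3 | 15-21 | 63-69 | 14-20 | 7 |
| 4 | 22-28 | 70-76 | 21-27 | 7 |

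Period 2 weeks 3 and 4 each start one day early. Ranges of 57-63, 64-70 and 71-77 restore treatment days 8-14, 15-21 and 22-28.

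**3. Evenings already rated when Visit 7 takes place, window held fixed.**

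| Visit 7 on | Days 71-77 (Protocol 9.1) | Days 70-76 (SAP 10.3) |
|---|---|---|
| Day 76 | 5 | 6 |
| Day 77 | 6 | 7 |
| Day 78 | 7 | 7 |

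**4. Chance that week 4 is set to missing.** Neither document gives a daily completion rate. I assume evenings are missed independently with probability 2% to 15%. With k evenings available, P(missing) = 1 − P(X ≥ 5), X ~ Binomial(k, 1 − missed rate).

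| Missed per evening | k = 7 | k = 6 | k = 5 | Extra missing of 44, k = 6 v 7 |
|---|---|---|---|---|
| 2% | 0.03% | 0.57% | 9.6% | 44 × 0.0054 = 0.2 |
| 5% | 0.38% | 3.28% | 22.6% | 44 × 0.0290 = 1.3 |
| 10% | 2.57% | 11.43% | 41.0% | 44 × 0.0886 = 3.9 |
| 15% | 7.38% | 22.35% | 55.6% | 44 × 0.1497 = 6.6 |

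**5. Effect on power, complete pairs only.** Expected pairs = 44 × P(period 1 value present) × P(period 2 value present).

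| Missed | Pairs, 7 + 7 evenings | Pairs, 7 + 6 evenings | Power, 7 + 7 | Power, 7 + 6 |
|---|---|---|---|---|
| 5% | 43.7 | 42.4 | 0.898 | 0.889 |
| 10% | 41.8 | 38.0 | 0.884 | 0.851 |
| 15% | 37.7 | 31.6 | 0.849 | 0.777 |

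This overstates the cost, because the model in SAP 11.6.1.2 fits weeks 1 to 4 of both periods together and keeps a subject's other weeks.

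**The case against.** The strongest reply is that the plan as printed loses nothing at a nominal visit. The five-rating minimum is an SAP rule, and the SAP's own Period 2 week 4 ends on Day 76, so all seven evenings precede a Day 77 visit. That is correct, and a reader should not infer that the printed SAP window drops a rating at that visit. It does not rescue the plan, because the same range conflicts with SAP 7.1 and leaves the two periods one treatment day apart.

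The second reply is that non-collection is read from silence. Visits 3, 4, 6 and 7 also ask only for the bottle, yet the diary is checked there. Nothing says the diary is surrendered at Visit 7, and a row that records ratings would naturally be blank at Visit 8. This stands: the documents do not show that the Day 77 entry is lost. They show that no step provides for its return, whereas after Visit 4 subjects are told to continue entries and bring the diary on Day 50.

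Three stronger inferences also fail:
- **At most six evenings in Period 2.** A Day 78 visit allows seven.
- **Five evenings as a typical case.** Five needs a Day 76 visit with Days 71-77 held fixed. If the period is taken to end at the visit, as 8.6.3 describes Visit 7, only one evening is lost.
- **Distortion from visit-day procedures.** The morning dose is taken at the clinic, the paracetamol limit covers only 4 hours around the visit, and both apply in each period.

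**Conclusion.** The point holds in a limited form. It is certain from the text that SAP 10.3 does not match Protocol 9.1 and SAP 7.1, and that week 4 covers treatment days 22-28 in Period 1 but 21-27 in Period 2. It is also certain that neither document states how an evening entry made after the Day 77 visit reaches the site.

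The size of any loss is conditional. It rests on SAP 10.3 being corrected to Days 71-77, on the Day 77 entry not being retrieved, on a nominal visit date, and on an assumed rate of independently missed evenings. Under those conditions the extra missing Period 2 values run from about 0.2 of 44 subjects at 2% missed to about 7 at 15%.

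A reader might infer a bias towards one treatment. The documents do not support that: the loss falls on Period 2 in both sequences. The cost is some precision, partly recovered by the mixed model, and poorer comparability between periods. The point is worth correcting because it touches the primary endpoint and the correction is nearly free.

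**What to change.** 1. In SAP 10.3, change the Period 2 ranges for weeks 2, 3 and 4 to Days 57-63, 64-70 and 71-77.
2. In Protocol 8.6.3, tell subjects to make the Day 77 evening entry and bring the diary to Visit 8. Add diary return to 8.7.1 and to schedule 2.2 (and its copy in SAP 5.2).
3. In Protocol 8.6 and the synopsis, have the diary returned on Day 50 cover Days 28 to 49.
4. Reconcile the synopsis's morning entry on Days 28 and 77 with evening-only rating, so that a site does not close the diary with a morning score.

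The cost is wording and one extra item to collect at an existing visit.

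An alternative is to end the window on the evening before the visit in both periods (nominally Days 21-27 and 70-76). Every rating is then in hand at the nominal visit. This changes the endpoint definition in Protocol 9.1 and SAP 7.1, and all week ranges must be redrawn, since Day 21 already belongs to week 3 (Days 15-21). Only 27 treatment evenings precede the nominal visit, so four 7-day weeks (28 evenings) do not fit without overlap and one week would have six. The first option is cleaner.
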